**NCT Number: 03325790** 

# **1 PROTOCOL SUMMARY**

# 1.1 Synopsis

[figure not shown]
| SPI-1005-251: CLINICAL TRIAL SYNOPSIS |   |  |  |  |  |
|---------------------------------------|---|--|--|--|--|
| Title                                 | A PHASE 2b, RANDOMIZED, DOUBLE-BLIND, PLACEBO-
CONTROLLED STUDY TO EVALUATE THE SAFETY AND
EFFICACY OF SPI-1005 IN MENIERE'S DISEASE  |  |  |  |  |
| Study                                 | The primary objective of this Phase 2 study is to determine the:  |  |  |  |  |
| Objective(s)                          | • Safety of SPI-1005 treatment in adults with Meniere's disease.  |  |  |  |  |
|                                       | • Efficacy of SPI-1005 will be determined by the following clinically significant methods and measures (responder analysis):  |  |  |  |  |
|                                       | 
 
> Pure tone audiometry (≥30 dBHL at 250, 500 or 1000 Hz)
 
≥10 dB improvement from baseline
 
> Words in Noise Test (0-35)
 
  |  |  |  |  |
|                                       | 
 
≥10 % increase from baseline
 
➤ Tinnitus Functional Index (TFI) (0-100)
 
   |  |  |  |  |
|                                       | $\geq$ 10 pt. reduction from baseline   |  |  |  |  |
|                                       | 
 
Tinnitus Loudness: Q#2 of TFI (0-10)
 
2 pt. reduction from baseline
 
   |  |  |  |  |
|                                       | 
 
Vertigo Symptom Scale (0-60)
 
26 pt. reduction from baseline
 
  |  |  |  |  |
|                                       | 
 
The responder analysis from each method and measure will be compared between treatment groups for significance.
 
Efficacy of SPI-1005 treatment in adults with Meniere's disease based on 
 
Improvement in sensorineural hearing loss using pure tone audiometry at 250, 500, or 1000 Hz; or
 
Word recognition score using WIN testing at 24, 20, 16, 12, 8, 4 and 0 SNR; or
 
 
 
 |  |  |  |  |
|                                       |   |  |  |  |  |
|                                       |   |  |  |  |  |
|                                       | • Improvement in the Tinnitus Functional Index (TFI); or  |  |  |  |  |
|                                       | • Improvement in Tinnitus Loudness (TL); or   |  |  |  |  |
|                                       | • Improvement in the Vertigo Symptoms Scale (VSS).  |  |  |  |  |
|                                       | The secondary objectives of this study are to determine the:  |  |  |  |  |
|                                       | • Pharmacokinetics of SPI-1005.   |  |  |  |  |
| Study Design                          | Randomized Double Blind Placebo Controlled Study of SPI-1005 in adult volunteers with Meniere's Disease (probable or definitive   |  |  |  |  |

| SPI-1005-251: CLINICAL TRIAL SYNOPSIS |   |  |  |  |
|---------------------------------------|---|--|--|--|
|                                       | diagnosis) with active symptoms in the months preceding study
enrollment. All subjects will undergo baseline audiometric testing and
have their severity of sensorineural hearing loss, tinnitus and vertigo
determined before initiating treatment. Subjects will be randomized to
treatment, either placebo or two different doses of SPI-1005 (1:1:1)
and treated for 28 days. Subjects will return to clinic 2 weeks after the
start of study drug to have safety assessments and to receive additional
study drug. Subjects will return to clinic at week 4 to have their
hearing loss, tinnitus and vertigo re-assessed, and again 4 weeks after
the end of study drug treatment. Therefore, 4 scheduled clinic visits
will be performed over an 8 week period. Audiometry will be
performed at baseline, at the end of the 4 week treatment period, and 4
weeks after treatment has stopped. The TFI and VSS will be
performed at all scheduled clinic visits. Subjects are allowed to
continue with their existing maintenance therapies (i.e. low salt diet,
thiazide diuretic, or other PRN medications) except for the use of oral
or locally injected steroids. New treatments should be avoided while
on study. |  |  |  |
| Study Centers                         | Approximately 12 U.S. sites will participate in this study  |  |  |  |
| Subjects                              | 120 male and female adults with probable or definitive Meniere's disease.   |  |  |  |
| Inclusion
Criteria                 | 
 
Adult male and female patients, 18-75 years of age at the time of enrollment.
 
Diagnosis of probable or definitive Meniere's disease by AAO-HNS 1995 criteria (Section 12.1, APPENDIX I).
 
Two of three active symptoms including vertigo or disequilibrium, fluctuating hearing loss, or tinnitus within the 3 months prior to study enrollment.
 
Hearing loss of ≥30 dBHL at either 250, 500 or 1000 Hz.
 
Voluntary consent to participate in the study.
 
Male subjects that are willing to use condoms throughout the study period and 90-days following study completion even if not fertile.
 
Females of childbearing potential should either be sexually inactive (abstinent) for 14 days prior to screening and throughout the study or be using one of the following acceptable birth control methods: 
 
IUD in place for at least 3 months prior to study; or
 
Barrier method (condom or diaphragm) with spermicide for at least 14 days prior to screening through study completion; or
 
Stable hormonal contraceptive for at least 3 months prior
 
 
 
   |  |  |  |

| SPI-1005-251: CLINICAL TRIAL SYNOPSIS |  |  |  |  |
|---------------------------------------|--|--|--|--|
|                                       | 
 
to study and through study completion; or
 
Surgical sterilization (vasectomy) of partner at least 6 months prior to study enrollment.
 
Females of non-childbearing potential should be surgically sterile (bilateral tubal ligation with surgery at least 6 months prior to study enrollment, hysterectomy, or bilateral oophorectomy at least 2 months prior to study) or be at least 1 year since last menses.
 
 |  |  |  |
| Exclusion
Criteria                 |  |  |  |  |
| Study Duration                        | Estimated duration of 12 months  |  |  |  |
| Participant
Duration               | Participation for each study participants will be approximately 8 to 12 weeks across 4 clinic visits.  |  |  |  |
| Dose &
Regimen                     | Subjects will receive either SPI-1005 or matching placebo for 28 days.
Treatment will be taken orally BID. Doses include 200 mg or 400 mg
of ebselen or matching placebo in capsule form. Two week supplies
will be provided on Clinic Visit 1 and 2.   |  |  |  |

| SPI-1005-251: CLINICAL TRIAL SYNOPSIS |   |  |  |  |
|---------------------------------------|---|--|--|--|
| Safety &
Tolerability              | Physical examinations, vital signs, adverse events, hematology (CBC) and serum chemistries will encompass safety assessments.                       |  |  |  |
| Assessments                           | Adverse events will be coded using MedDRA (Version 18.1 or higher) and summarized by treatment group for the number of adverse events and compared. |  |  |  |
|                                       | Vital signs and clinical laboratory results will be summarized for each treatment group and compared.   |  |  |  |
| PK
Assessments                     | The trough plasma levels of ebselen and its major metabolite (2-glucuronyl selenobenzanilide) will be determined using LC-MS/MS.                    |  |  |  |
|                                       | The corresponding selenium plasma levels will be determined by ICP-MS.  |  |  |  |
|                                       | PK results will be summarized by treatment group.   |  |  |  |
| Lead
Investigator (s)              | [name]   |  |  |  |

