#### 6.2.1 Primary Parameter

- Efficacy of SPI-1005 will be determined by the following clinically significant methods and measures (responder analysis):
- ➤ Pure-tone audiometry assessment (250, 500 or 1000 Hz): Improvements from baseline of ≥10 dB at 1 frequency
- ▶ Words-in-Noise Test assessment (0-35): Improvements from baseline of  $\geq 10\%$ 
  - Tinnitus Functional Index (TFI) (0-100) ≥ 10 pt. reduction from baseline

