#### 7.3.2 Intent-to-Treat (ITT) Analysis Population

The ITT Efficacy Analysis population includes all patients from the randomized population who have received at least one dose of study drug and who have an evaluated post baseline efficacy assessment. The efficacy assessments include the evaluation of:

- Non- missing Pure-tone audiometry at Visit 3 or Visit 4
- Non- missing Words-in-Noise Test at Visit 3 or Visit 4
- Non-missing Tinnitus Functional Index (TFI) at Visit 2 or Visit 3 or Visit 4
- Non-missing Tinnitus Loudness (TL) at Visit 2 or Visit 3 or Visit 4
- Non-missing Vertigo Symptom Scale (VSS) at Visit 2 or Visit 3 or Visit 4

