#### **Confidentiality Statement**

Version No.: Final 1.0

A ECRON ACUNOVA

Sponsor Study No: SPI-1005-251

Sponsor Name: Sound Pharmaceuticals, Inc.

NLS Study Code: SPI-1005-251

Short Title of Study: SPI-1005-251 (Sound Pharmaceuticals, Inc)

The major protocol deviations include:

- Treatment compliance of <80% and >120%
- Did not meet inclusion/exclusion criteria
- Baseline overall WINT score ≥ 2x Standard Deviations above the mean (rounded down to nearest integer)
- Major protocol deviations impacting the primary efficacy outcome measure.

Page 15 of 38

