#### 7.6 Sample Size Calculation

120 male and female adults with probable or definitive Meniere's disease. This Phase 2b study (SPI-1005-251), is adequately powered to demonstrate a 50% improvement in a symptom of MD using the responder analysis detailed in below with 40 study participants per treatment group.

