The TFI data will be analyzed with a mixed-effects model for repeated measures, and a post-hoc Bonferroni correction analysis with significance set to 0.05. The calculated change of TFI data will be calculated as the difference of the PRO value at baseline and the PRO value at each post baseline timepoint. The improvement will be considered only if the difference between post baseline and baseline value is  $\geq 10$  pts. The final processed data will be analyzed using a chi-square test or Fisher's Exact test to assess the improvement between treatment groups.

This document is confidential and proprietary to Sponsor and EA and for restricted circulation and access only. No part of it may be transmitted, reproduced, published or used by any person/s without prior written authorization.

Statistical Analysis Plan Version No.: Final 1.0

Page 22 of 38

Sponsor Study No: SPI-1005-251 Sponsor Name: Sound Pharmaceuticals, Inc.

CRON ACUNOVA

NLS Study Code: SPI -1005 -251

Short Title of Study: SPI-1005-251 (Sound Pharmaceuticals, Inc)

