#### 8.3.1.5 Vertigo Symptom Scale

Vertigo Symptom Scale (VSS) will be measured at visit 1, visit 2, visit 3 and visit 4.

The actual patient reported outcome (PRO) value and change from baseline for VSS will be summarized by visits and treatment groups.

VSS will be analyzed for Total Scale, Vertigo/balance sub-scale and Autonomic/anxiety sub-scale. The Vertigo/balance sub-scale will be calculated as the sum of questions 1, 3, 4, 6, 8, 10, 13 and 15. The Autonomic/anxiety sub-scale will be calculated as the sum of questions 2, 5, 7, 9, 11, 12 and 14. The range for the Vertigo/balance sub-scale will be 0 - 32 and the range for Autonomic/anxiety sub-scale will be 0 - 32.

VSS data will be analyzed with a mixed-effects model for repeated measures, and a post-hoc Bonferroni correction analysis with significance set to 0.05.

The calculated change of VSS data will be calculated as the difference of the PRO value at baseline and the PRO value at each post baseline timepoint. The improvement will be considered only if the difference between post baseline and baseline value is  $\geq 6$  pts. The final processed data will be analyzed using a chi-square test or Fisher's Exact test to assess the improvement between treatment groups.

This document is confidential and proprietary to Sponsor and EA and for restricted circulation and access only. No part of it may be transmitted, reproduced, published or used by any person/s without prior written authorization.

Version No.: Final 1.0

ECRON ACUNOVA Sponsor Study No: SPI-1005-251 Sponsor Name: Sound Pharmaceuticals, Inc.

NLS Study Code: SPI-1005-251

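### Patients whose baseline TFI, TL or VSS score is too low to allow a response may be randomised and stay in the responder denominator, which shrinks the absolute difference and costs power

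*Protocol*

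**What the plan says.** **Entry (Protocol 1.1, Inclusion Criteria).** Patients need "Two of three active symptoms including vertigo or disequilibrium, fluctuating hearing loss, or tinnitus within the 3 months prior to study enrollment". Any one of the three may be absent, and those present need only have been active at some time in the window. The list sets a measured floor for hearing alone: "Hearing loss of ≥30 dBHL at either 250, 500 or 1000 Hz". It names no minimum TFI, TL or VSS score.

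**Responder rules (SAP 6.2.1, 8.3.1.3 to 8.3.1.5).** One primary measure is "Tinnitus Functional Index (TFI) (0-100) ≥ 10 pt. reduction from baseline". TL needs a fall of at least 2 on 0-10, and VSS at least 6 on 0-60. For TFI the SAP says "The improvement will be considered only if the difference between post baseline and baseline value is" at least 10 points, and the TL and VSS sections use the same wording with their own thresholds.

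**Analysis sets (SAP 7.3.2, 7.3.4).** ITT comprises "all patients from the randomized population who have received at least one dose of study drug and who have an evaluated post baseline efficacy assessment". Per-Protocol requires treatment, Visit 3 efficacy data and no major deviation. The only baseline efficacy score in the list of major deviations is a high one on the Words-in-Noise Test: "Baseline overall WINT score ≥ 2x Standard Deviations above the mean (rounded down to nearest integer". Responder tables are planned for these two sets only (SAP 13), and SAP 8.7 plans no subgroup analyses.

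**Sample size (SAP 7.6).** With 40 per group the study "is adequately powered to demonstrate a 50% improvement in a symptom of MD using the responder analysis". No response rates or power value are given.

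**The concern.** A score cannot fall by more points than it starts with. Read together, the entry rule, the thresholds and the analysis sets leave room for patients who cannot be responders whatever they receive. Each one adds to the denominator and nothing to the numerator.

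What is at stake is the size of the reported absolute benefit on the two tinnitus measures and the vertigo measure, and the power of the three chi-square or Fisher tests. The shrinkage depends on the share below threshold, which may differ between TFI, TL and VSS and is not planned to be reported.

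The plan already attends to the baseline score on the hearing side. Audiometry has an entry floor, and Per-Protocol removes patients with very high Words-in-Noise scores, who have limited room to improve. The three patient-reported measures have no counterpart.

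**Working it through.** **1. The plan's own figure.** The 40 per group cannot be reproduced, because SAP 7.6 gives neither response rates nor power. The formula used is the pooled two-proportion one, two-sided 0.05 (SAP 7.1), n per arm, with p̄ the mean of p1 and p2:

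power = Φ{ [ |p2 − p1|·√n − 1.96·√(2p̄(1 − p̄)) ] / √(p1(1 − p1) + p2(1 − p2)) }

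At n = 40, the possible meanings of a 50% improvement give:
- Relative gain of half: 20% v 30%, power 17.5%; 40% v 60%, 43.1%; 60% v 90%, 88.8%.
- Absolute gain of 50 points: above 99%.
- 50% response on active: v 20% on placebo, 81.6% (39 per arm for 80% power); v 30%, 44.5%.

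The closest match to 40 is 20% v 50%, but that placebo rate is an assumption.

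**2. Who cannot respond.** The condition is baseline minus threshold below zero: TFI < 10, TL < 2 or VSS < 6. It concerns the score, not the symptom label. The VSS has 15 items and a 0-60 range, so 60/15 = 4 points per item. SAP 8.3.1.5 states that "The Autonomic/anxiety sub-scale will be calculated as the sum of questions 2, 5, 7, 9, 11, 12 and 14". Those seven items can reach 7 × 4 = 28, so a patient with no vertigo can still start at 6 or more and respond.

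**3. What such patients do to the result.** Let f be the share of each arm below threshold. With everyone counted, both rates are multiplied by (1 − f), and so is their difference. Example with 30% v 60% among those able to respond, 40 per arm, f = 20%:
- Able to respond: 40 × 0.8 = 32 per arm.
- Expected responders: 0.3 × 32 = 9.6 and 0.6 × 32 = 19.2.
- All 40 counted: 9.6/40 = 24% v 19.2/40 = 48%; difference 24 points, ratio 2.
- Only the 32 counted: 30% v 60%; difference 30 points, ratio 2.

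**4. Power.** Exact enumeration of the uncorrected chi-square test for 30% v 60% (assumed). Power is 80% if everyone can respond.

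| f | Rates, all 40 | Difference | Power, all 40 | n able to respond | Power, restricted |
|---|---|---|---|---|---|
| 10% | 27% v 54% | 27 points | 71% | 36 | 73% |
| 20% | 24% v 48% | 24 points | 61% | 32 | 71% |
| 30% | 21% v 42% | 21 points | 52% | 28 | 61% |

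**5. Cross-check by the formula in step 1, f = 20%.**
- All 40: (0.24 × 6.325 − 1.96 × 0.679)/0.657 = 0.285, power 61.2%.
- Restricted to 32: (0.30 × 5.657 − 1.96 × 0.704)/0.671 = 0.474, power 68.2%.

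The direction is the same. The gain is 7 points by this formula and about 10 by exact enumeration, because the exact test moves in steps at these sample sizes.

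**6. Sensitivity to the assumed rates (exact, f = 10% to 30%).** Power gained by restricting:
- 20% v 30%: 0 to 1 point.
- 30% v 45%: 2 to 3.5 points.
- 40% v 60%: nil at f = 10%, 5 to 8 points at 20% to 30%.
- 50% v 75%: 5 to 13 points.

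**The case against.** The strongest reply is that the all-patient denominator answers the question asked. Protocol 1.1 and SAP 5.1 speak of efficacy in adults with Meniere's disease, on five measures joined by or. Restricting the denominator narrows the target population. The loss falls equally on all arms in expectation, and TFI, TL and VSS are also analysed as continuous scores by a mixed model, so the responder test is not the only evidence. All of this stands. It argues for keeping the all-patient result, not for leaving the shrinkage unreported.

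A reader might infer more than the documents support:
- *Every patient lacking a symptom must fail on its measure.* This is close to true for TFI and TL, but not for VSS, given its autonomic/anxiety items and an entry criterion that accepts disequilibrium.
- *The objective is benefit in patients who have the symptom.* The stated population is adults with Meniere's disease.
- *SAP 7.6 assumes all 40 have each symptom.* It refers to study participants and to a symptom; it does not say this.
- *The five response rates become non-comparable, to the harm of the analysis.* The SAP compares treatment groups within each measure, never rates across measures.
- *The trial is biased towards one arm.* It is not; the effect is dilution.

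Two limits on the evidence also stand. The SAP never states the responder denominator in words; counting these patients as non-responders is inferred from the set definitions and the threshold rule. The exclusion criteria, the diagnostic appendix and some SAP pages are not in the text available, so a floor stated there cannot be ruled out.

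**Conclusion.** The point holds as a mismatch between the baseline score and the response threshold. Nothing in the available text stops a patient with TFI below 10, TL below 2 or VSS below 6 from entering, and nothing removes that patient from the responder analysis. The cost is an absolute difference multiplied by (1 − f) and some loss of power.

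Its size is uncertain. Both f and the response rates are assumptions. Across the scenarios tried, restricting the denominator gains between about 0 and 13 points of power. At 30% v 60% it gains about 2, 10 and 9 points for f of 10%, 20% and 30%. A material loss is possible but not shown. Restriction does not recover everything: at f = 20% it gives 71%, against 80% if all 40 could respond. The change is worth making because it is cheap and follows a principle the plan already applies to hearing.

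**What to change.** In SAP 6.2.1 and 8.3.1.3 to 8.3.1.5, before unblinding:

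1. Define a responder-evaluable set for each measure: baseline TFI ≥ 10, TL ≥ 2 or VSS ≥ 6, with baseline as in SAP 7.8. Describe it as patients whose baseline score allows a response, not as patients who have the symptom.
2. Report the responder comparison in that set alongside the all-patient ITT and Per-Protocol comparisons, stating each denominator in words.
3. Give the number below threshold per arm for each measure.
4. Name in advance which comparison leads.

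If a baseline floor already exists in text not available here, a reference to it would settle the matter.

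The entry criteria need not change and no new data are needed: TFI (which contains the TL item) and VSS are both collected at Clinic Visit 1. Because each set is fixed by pre-treatment scores, the randomised comparison within it stays valid. The cost is SAP wording, an extra denominator per table, a smaller n, and a narrower target population for those three measures.

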### 1.2 Schema

#### **Schedule of Assessments** 1.3

| Clinic Visit                         | CV1
(Screening/Baseline) | CV2        | CV3        | CV4       |
|--------------------------------------|-----------------------------|------------|------------|-----------|
| Study Day                            | -28 to 1                    | 14 (+/- 3) | 28 (+/- 3) | 56 (+/-3) |
| Informed
Consent                  | Х                           |            | . ,        |           |
| Demographics                         | Х                           |            |            |           |
| Medical
History                   | Х                           |            |            |           |
| Physical Exam                        | Х                           | Х          | Х          | Х         |
| Hight                                | Х                           |            |            |           |
| Weight                               | Х                           | Х          | Х          | Х         |
| BMI                                  | Х                           |            |            |           |
| Vital Signs                          | Х                           | Х          | Х          | Х         |
| CBC                                  | Х                           | Х          | Х          | Х         |
| Serum
Chemistry                   | Х                           | Х          | Х          | Х         |
| Urine
Pregnancy     | Х                           |            |            |           |
| Otoscopy                             | Х                           |            | Х          | Х         |
| Tympanometry                         | Х                           |            |            |           |
| TFI                                  | Х                           | Х          | Х          | Х         |
| VSS                                  | Х                           | Х          | Х          | Х         |
| РТА                                  | Х                           |            | Х          | Х         |
| WINT                                 | Х                           |            | Х          | Х         |
| Concomitant
Medication
Review  | Х                           | Х          | Х          | Х         |
| Randomization                        | Х                           |            |            |           |
| SPI-1005
Treatment  | Х                           | Х          | Х          |           |
| Adverse Events                       | Х                           | Х          | Х          | Х         |
| PK                                   | Х                           | Х          | Х          | Х         |

 Urine pregnancy test on CV1 screening visit only.
  SPI-1005 treatment begins after safety labs (CBC, serum chemistry) are reviewed and all inclusion/exclusion criteria are met.
